### 6.2.6 Subgroup analysis

Subgroup analyses for the efficacy and safety outcomes will be performed based on the same analysis sets and data scopes as in the main analyses of the study outcomes. The subgroup analyses will be presented descriptively without formal hypotheses testing. Additionally forest plots will be generated.

Homogeneity of treatment effect in subgroups, both in magnitude and direction, will be assessed by adding a covariate for the subgroup variable and the corresponding treatment-subgroup interaction to the respective (age-group stratified) Cox proportional hazards model used in the main analysis. Additionally the hazard ratio for the treatment effect will be estimated separately within each level of a subgroup variable using the same Cox proportional hazards.

As the number of subgroup analyses may be large, the probability of observing at least one spurious interaction is high despite the lack of a biological or pharmacological basis for expecting an interaction. Thus, any interactions with a p-value below the 5% type I error level in the analysis of primary outcomes will be interpreted as “flags” to prompt further

investigation into the consistency of the pattern within secondary and related outcomes. This further investigation includes the likelihood ratio test proposed by [Gail](#) to test for qualitative interaction.

### **6.2.7 Sensitivity analyses - amended**

To support the primary study results and to assess to robustness of the primary analysis several sensitivity analyses will be performed ([Little](#)).

The analysis of the primary and secondary efficacy variables as described in section [6.2.4](#) and [6.2.5](#) will be repeated based on the safety analysis set using the on-treatment data scope.

The analysis of the primary and secondary efficacy variables as described in section [6.2.4](#) and [6.2.5](#) will be repeated counting outcome events as reported by the investigators.

The analysis of the primary and secondary efficacy variables as described in section [6.2.4](#) and [6.2.5](#) will be repeated using the Cox proportional hazard model without stratification.

The analysis of the primary and secondary efficacy variables as described in section [6.2.4](#) and [6.2.5](#) will be repeated counting adjudicated outcome events up to the last trial contact date, i.e. including also events after the efficacy cut-off date.

Despite all efforts it will be hard to completely avoid loss to follow-up within this study ([White](#)).

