## 4.5 Data Rules

### 4.5.1 Analysis Dates - amended

For the study the following date and time window are of relevance for the analysis:

- Efficacy cut-off date:  
The efficacy cut-off date is the 5th of October 2017, the date the early stopping of the trial was officially announced.
- Trial close-out window:  
The Trial close-out window is the time period when all subjects are to return to the clinic for an End of treatment Visit.

For each subject, the following individual dates are of relevance for analysis:

- Randomization date:  
The date of randomization to antithrombotic study treatment of the subject.
- End of treatment (EOT) Visit date:  
This is the date of the EOT Visit for the individual subject.  
After the announcement of the end of the study, all subjects are to return to the clinic for their EOT Visit within the pre-specified window (Trial close-out window).  
If subjects do not have an EOT visit, the date will be missing.
- Date of the last contact prior or equal to efficacy cut-off:  
This date is defined as the date of the last trial contact or the efficacy cut-off date, whatever comes first.
- Date of the last trial contact:  
The date of the last documented contact with the subject or a third party (including data on subject survival status).  
For subjects who die after randomization the date of the last contact is set to the death date.
- Date of first double-blind dose of antithrombotic study treatment:  
The date of the first dose of rivaroxaban / aspirin study medication.
- Date of last double-blind dose of antithrombotic study treatment:  
The date of the last dose of rivaroxaban / aspirin study medication.  
For a subject with permanent discontinuation of any study medication, the corresponding last dose date(s) will be obtained from the CRF "Study Medication Discontinuation/Restart Report". If study medication was continued until the EOT visit, the date of the last dose of the corresponding study medication will be as reported on the EOT visit CRF.  
If missing or incomplete, the date of last double-blind dose of antithrombotic study

treatment is set to the latest logically possible date of antithrombotic study medication administration on or before the earliest of the subject's following dates, the date of last trial contact, the date of death, or the efficacy cut-off date, and no earlier than the randomization date.

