##### **Data scope according to intention-to-treat principle (ITT)**

The ITT data scope includes all outcome events observed from randomization until the efficacy cut-off date. This will be the primary data scope for the analyses.

Analyses according to the intention-to-treat (ITT) principle will be based on the intention-to-treat analysis set (see section 5.1.1) and will include all outcome events that occur from the date of randomization and up until the efficacy cut-off date (inclusive). Subjects will be kept in the study group to which they were randomized and the follow-up period for each subject will be as long and complete as possible. This ITT data scope will be applied to the primary analysis of the primary and secondary efficacy variables and safety variables.

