#### **4.5.3 Censoring rules for time-to-event variables - amended**

For any time-to-event variable in this study, the following censoring rules will be applied:

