##### **Censoring rules for analyses according to the intention-to-treat principle**

For analyses according to the intention-to-treat principle, randomized subjects without documentation of an event will be censored at the efficacy cut-off date or the date of the last trial contact, whatever comes first.

This censoring rule will be applied to all analyses according to the intention-to-treat principle. In the rare event that for a subject only survival status information can be retrieved at the end

of the study but no information on other outcomes, the last follow-up / trial contact where survival status information was obtained will still be used to determine the censoring date for the subject and if there were no known events up to then the subject will be considered as event-free.

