Subjects without a primary efficacy outcome event will constitute a right-censored observation (see section 4.5.3 for censoring rules). Primarily, for the time-to-event analysis the censoring mechanism will be assumed to be non-informative. Additional sensitivity analyses will be performed in order to evaluate the robustness of the statistical results under different assumptions (see section 6.2.7).

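### The last-contact sensitivity analysis in SAP 6.2.7 counts events after the cut-off, but the only ITT censoring rule stops event-free patients at the cut-off, which inflates its late cumulative-risk curves (minor)

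*SAP*

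**What the plan says.** Four parts of the SAP bear on this.

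- **Event window of the added analysis (6.2.7).** The analyses of 6.2.4 and 6.2.5 are "repeated counting adjudicated outcome events up to the last trial contact date, i.e. including also events after the efficacy cut-off date". No censoring date is given.
- **Censoring (4.5.3).** The section opens with "For any time-to-event variable in this study, the following censoring rules will be applied". Under the ITT rule, patients without an event "will be censored at the efficacy cut-off date or the date of the last trial contact, whatever comes first". It then adds: "This censoring rule will be applied to all analyses according to the intention-to-treat principle". The only other rule is for on-treatment analyses.
- **Link between the two (6.2.4).** The primary analysis, which 6.2.7 repeats, sends the reader to 4.5.3 for the censoring of event-free patients.
- **Dates (4.5.1).** The cut-off is 5 October 2017, "the date the early stopping of the trial was officially announced". The date of last trial contact is defined separately for each patient and can be later, because end-of-treatment visits follow the announcement and SAP 3 places a telephone safety visit one month after that visit.

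The overview of SAP Amendment 2 (7.2) shows that both changes came together: ITT scope and censoring were tied to the new cut-off, and the last-contact analysis was added and described only by its event window.

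**The concern.** A time-to-event analysis needs the same end of observation for patients with and without the event. Elsewhere the SAP respects this. The ITT scope and its censoring both end at the cut-off, and the on-treatment scope and its censoring both extend two days past the last dose. The last-contact analysis is the exception: its event window was extended and its censoring was not.

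If the wording is followed, a patient seen after 5 October 2017 contributes that later time only by having an event. Length of follow-up then depends on the outcome. The same would happen for each secondary outcome, since 6.2.7 repeats those analyses too.

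At stake are the absolute risks and curves of one sensitivity analysis. Because the trial stopped early, readers will look at events after the stop. A curve that climbs above the primary one through a censoring artefact could be mistaken for a real rise in risk after stopping.

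**Working it through.** **Inputs from SAP 4.6:** 7000 patients 1:1; 2-year accrual, 3-year study; aspirin event rate 3.8% per year; expected observed relative risk reduction 26% (hazard ratio 0.74); deaths 3% and loss 1% per year; about 450 events for 90% power at one-sided 0.025.

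**Assumptions:** uniform accrual; last contact a fixed 2, 6 or 10 weeks after the cut-off; both arms at the aspirin hazard after the cut-off. Ten weeks is the 6-week return period in Protocol 7.1.2.4 plus about one month to the safety call. SAP 4.5.1 gives the close-out window no length.

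**Anchor to the plan's own figure.** Schoenfeld: z = ½ × √450 × |ln 0.74| − 1.96 = 10.607 × 0.3011 − 1.96 = 1.23, so power is 89.1% (90.4% at a hazard ratio of 0.735, which also rounds to about 26%). Expected events under the stated accrual, event, death and loss rates: 249.4 + 186.5 = 435.9. The plan's figures are consistent and are not in dispute.

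**Direction and size by hand.** With uniform accrual, time from randomization to cut-off is spread evenly over 1 to 3 years. At time t, a share (3 − t)/2 of patients has not yet reached the cut-off. With a window of w years, a further share w/2 lies between cut-off and last contact (for t ≥ 1 + w). Literal censoring counts events from both groups but keeps, from the second group, only those who will have an event. The estimated hazard at t is therefore multiplied by about 1 + w/(3 − t). For w = 10/52.18 = 0.192, the factor is 1.19 at 2 years, 1.38 at 2.5 years and 2.9 at 2.9 years.

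With λ = −ln(1 − 0.038) = 0.0387, the excess cumulative hazard at 2.5 years is

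λ × { [2 ln(2/(2 − w)) − w] + w ln((2 − w)/0.5) }

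The first bracket covers the build-up from 1 to 1 + w years. Event-free probability at 2.5 years is exp(−0.0387 × 2.5) = 0.908.

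| Window | Braces | Excess hazard | Excess risk at 2.5 y |
|---|---|---|---|
| 2 weeks | 0.0004 + 0.0524 = 0.0528 | 0.0020 | 0.19 points |
| 6 weeks | 0.0034 + 0.1526 = 0.1560 | 0.0060 | 0.55 points |
| 10 weeks | 0.0098 + 0.2464 = 0.2562 | 0.0099 | 0.90 points |

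**Simulation (300 trials per window, aspirin arm, hazard ratio 0.74).** Matched means event-free patients are censored at last contact. Literal means they are censored as 4.5.3 says. Both count events to last contact.

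| Window | Events: primary / to last contact | 1-y risk, matched / literal | 2.5-y risk | 2.9-y risk | End of curve | Hazard ratio | Log-rank Z |
|---|---|---|---|---|---|---|---|
| 2 weeks | 435.3 / 444.2 | 3.78 / 3.78% | 9.23 / 9.42% | 10.57 / 10.96% | 10.97 / 13.91% | 0.746 / 0.746 | −3.06 / −3.06 |
| 6 weeks | 434.9 / 461.8 | 3.79 / 3.79% | 9.21 / 9.75% | 10.62 / 11.80% | 11.33 / 37.78% | 0.754 / 0.753 | −3.02 / −3.02 |
| 10 weeks | 434.0 / 478.4 | 3.79 / 3.79% | 9.19 / 10.08% | 10.59 / 12.50% | 11.59 / 65.26% | 0.761 / 0.761 | −2.96 / −2.96 |

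The 2.5-year differences (0.19, 0.54 and 0.89 points) agree with the hand calculation. There is no bias before year 1, because under planned accrual nobody reaches the cut-off earlier than that. The end of the curve fails because the risk set there is reduced to patients with late events. The drift of the hazard ratio from 0.74 to 0.76 is the same under both versions; it comes from the assumed return to the aspirin hazard after the cut-off, not from censoring.

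**The case against.** The best counter-argument is that 4.5.3 may not govern this analysis. SAP 4.5.2 says that ITT analyses "will include all outcome events that occur from the date of randomization and up until the efficacy cut-off date (inclusive"), so an analysis that deliberately goes past the cut-off could be said to lie outside that class. The date of last trial contact is already defined, 6.1.1 already plans a Kaplan-Meier plot of time to it, and a programmer could well take it as the end of observation. The separate output specifications, which are not available here, may say so. This stands as far as it shows that the error may never be coded. It does not remove the conflict: 4.5.3 speaks of any time-to-event variable, 6.2.4 points there, and nothing in the SAP states an exception. The programmer must either depart from the written rule or produce invalid curves.

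Several stronger readings are tempting and are not supported:

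- *That the treatment comparison is biased.* The error hits both arms alike; hazard ratio and Z barely move.
- *That this is the only planned look at close-out events.* The on-treatment analysis also takes in some of them. SAP 4.5.3 notes that an event within two days of stopping at the end-of-treatment visit counts there and not in the primary analysis, and that censoring matches.
- *That late events enter with no time at risk.* Those patients bring their own time. What is lost is the post-cut-off time of patients who stay event-free.
- *That a planned event rate per patient-year is wrong.* SAP 6.2.4 specifies no person-time rate; the outputs affected are the curves.

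**Conclusion.** The text is wrong as written, but the matter is minor. The event window in 6.2.7 and the only ITT censoring rule do not match, and literal application overstates cumulative risk in this one sensitivity analysis. The overstatement is about 0.2 to 0.9 percentage points for the aspirin arm at 2.5 years, grows to about 0.4 to 1.9 points at 2.9 years, and leaves the extreme tail unusable.

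These sizes rest on an assumed 2- to 10-week window, on planned rather than actual accrual, and on the planned event rate. The trial stopped before its planned end and the documents do not report the real follow-up, so the true figures may differ. The direction does not depend on those assumptions. The primary analysis, and any conclusion drawn from hazard ratios or log-rank tests, is essentially unaffected.

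**What to change.** In SAP 6.2.7, state that in the last-contact analysis subjects without an event are censored at the date of the last trial contact, as defined in 4.5.1. In 4.5.3, limit the sentence that applies the cut-off rule to every ITT-principle analysis to those that use the ITT data scope.

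Cost: one added sentence, one narrowed sentence and one extra censoring variable. No new data are needed and the primary analysis does not change. If the output specifications already censor at last contact, only the SAP wording needs to be aligned.

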## **6.3 Pharmacokinetics / pharmacodynamics**

Not applicable

## **6.4 Safety**

### **6.4.1 Adverse events - amended**

Adverse events (AEs) will be coded by MedDRA. The version number of MedDRA used for the analyses will be stored in the clinical database/system set-up. A listing will be provided linking the original investigator terms and the coded terms.

Analyses of reported adverse events will be performed based on the safety analysis set.

In case of uncertainty (e.g., missing or incomplete dates), adverse events will be classified as “treatment emergent” following the worst case approach.

An overall summary of SAEs and treatment-emergent (TE) AEs will be generated by treatment group and overall.

Incidences of subjects with TEAEs, drug-related and/or serious TEAEs, TEAEs causing discontinuation of study drug, and TEAEs of particular concern will be summarized by treatment group and overall grouped by MedDRA Primary System Organ Class (SOC) and Preferred Term (PT). In addition, the incidence of pre-treatment AEs and AEs during the follow-up will be tabulated.

Serious adverse events (SAEs), AEs leading to discontinuation and AEs of particular concern will be listed. The date, relative day (to study medication) and phase of the study (pre-treatment, during treatment, post-treatment) will be included.

Further summaries of SAEs by intensity and outcome will be provided, consistent with Bayer Global Medical Standards.

Adverse events matching the SMQ Haemorrhage terms (excl laboratory terms) will be excluded from the AE analysis to avoid double counting of events. This is affecting data from Japan where bleeding events are additionally reported as AEs. In general bleeding events are reported separately and analyzed as described in the following sections.

#### **6.4.2 Primary safety variable**

The primary safety variable is the time from randomization to time of first occurrence of a major bleeding (ISTH) defined as a bleeding event that meets at least one of the following criteria:

- Fatal bleeding, and/or
- Symptomatic bleeding in a critical area or organ (intracranial, intraocular, intraspinal, pericardial, retroperitoneal, intraarticular, or intramuscular with compartment syndrome), and/or
- Clinically overt bleeding associated with a recent decrease in the hemoglobin level of  $\geq 2$  g/dL (20 g/L; 1.24 mmol/L) compared to the most recent hemoglobin value available before the event, and/or
- Clinically overt bleeding leading to transfusion of 2 or more units of packed red blood cells or whole blood

#### **6.4.3 Secondary safety variables**

The secondary safety variables are the time from randomization to time of first occurrence of:

- Life-threatening bleeding, defined as a subset of major bleeding that meet at least one of the following criteria:
  - Fatal bleeding
  - Symptomatic intracranial bleeding
  - Reduction in hemoglobin of at least 5 g/dl (50 g/l; 3.10 mmol/L)
  - Transfusion of at least 4 units of packed red cells or whole blood
  - Associated with hypotension requiring the use of intravenous inotropic agents

- Necessitated surgical intervention
- Clinically relevant non-major bleeding, defined as non-major overt bleeding but
  - Requires medical attention (e.g., hospitalization, medical treatment for bleeding), and/or
  - Is associated with a study drug interruption of more than 14 days.
- Intracranial hemorrhage

#### **6.4.4 Other safety variables**

All bleeding events will be analyzed. In addition to the analysis according to ISTH as described above, bleeding events will be analyzed according to GUSTO, TIMI and BARC definitions.

Vital signs and weight will be analyzed descriptively.

Any pregnancy occurring in a study subject during the subject's participation in this study will be listed in the patient data listing.

#### **6.4.5 Analysis of safety variables**

The primary analysis of the safety variables will be based on the ITT analysis set using the ITT data scope. Additionally the safety variables will be analyzed based on the safety analysis set using the on-treatment data scope.

The primary and secondary safety variables will be tested parallel without control of the type I error level.

In order to evaluate whether rivaroxaban is different to ASA with respect to the time to a bleeding event in patients with ESUS, the following null hypothesis will be tested at the two-sided significance level of 0.05:

$$H_{0, B}: S_{RB}(t) = S_{AB}(t) \text{ for all time points } t \geq 0,$$

The two-sided alternative hypothesis will be:

$$H_{1, B}: S_{RB}(t) \neq S_{AB}(t) \text{ for at least one time point } t \geq 0,$$

where  $S_{RB}$  denotes the survival function of the rivaroxaban and  $S_{AB}$  denotes the survival function of the ASA group.

The analysis methods will be those described for the primary efficacy outcome.

The safety variables will be analyzed by subgroup as describe for the efficacy variables.

#### **6.5 Other procedures and variables**

The analysis of other variables will be by treatment group and overall and based on ITT.

Other variables are:

- Healthcare Resource Use
  - hospitalizations (total days length of stay, intensive care unit/cardiac care unit days, ward type); emergency room visits; unscheduled outpatient physician consultations; or visits related to bleeding, surgeries, other selected procedures (inpatient and outpatient); and post-stroke care (status of care, home health or rehabilitation center or long term care). Days off-work.
- European Quality of Life-5 Dimensions (EQ-5D)
  - EQ-5D is a standardized measure of health status developed by the EuroQol Group in order to provide a simple, generic measure of health for clinical and economic appraisal. Assessments will be done using both a descriptive system and the subject's self-rated health on a visual analogue scale where the endpoints are labeled 'Best imaginable health state' and 'Worst imaginable health state'.  
The following variables are of interest:
    - EQ-5D single dimensions
    - EQ-5D Visual Analogue Scale (VAS) values
    - EQ-5D index score
  - EQ-5D will be analyzed separate from section 14 of CSR.
- Montreal Cognitive Assessment (MoCA)
  - The Montreal Cognitive Assessment (MoCA) test assesses several cognitive domains: attention and concentration, executive functions, memory, language, visuoconstructional skills, conceptual thinking, calculations, and orientation. For each task correctly completed, one point is assigned. All subscores are summed up and adjusted for individuals with  $\leq 12$  years education to derive a total score ranging between 0 (for a totally cognitive impaired subject) and a maximum of 30 points (cognitively healthy participant).
- Standard Assessment of Global-Activities in the Elderly (SAGE)
  - The SAGE questionnaire comprises 15 items, each describing an activity for which the respondent has to indicate how much difficulty the subject has encountered in performing this activity in the past month. Regarding scoring for an item, 0 points are assigned if the participants endorse the "None/never performed" response, 1 point to the "Mild" response, 2 points to the "Moderate" response, and 3 points to the "Severe" response. One additional point will be assigned when in response to question 11, 12, and 15 the

respondent declares the need for help from another person or a tool to walk, jump the stairs or to bath. The total score will range from 0, describing a very independent participant over a broad spectrum of activities, to 48, describing a very dependent subject.

- Modified Rankin Score
  - The modified Rankin Score runs from 0-6, running from perfect health without symptoms to death.
  - The score will be analyzed by frequency tables and bar charts comparing baseline to EOT. Wilcoxon rank-sum test will be used to give exploratory p-values comparing treatment groups.

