5.1.2 Exclusion criteria - amended

1. Severely disabling stroke (modified Rankin score ≥ 4 at screening)
2. If imaging of intracranial arteries is performed by CT or MR angiography or transcranial Doppler: $> 50\%$ luminal stenosis or occlusion in arteries supplying the area of ischemia¹⁸
3. Patent foramen ovale with plans for closure
4. Known serious infection or inflammatory disease that may be the cause of stroke

¹⁴ Global Protocol Amendment 5 added the allowance of monitoring for at least 20 hours to reflect routine practice.

¹⁵ Transesophageal was added with global Protocol Amendment 5.

¹⁶ Prior to global Protocol Amendment 5, patients were eligible for inclusion if they were ≥ 18 years of age (or > 18 years based on country). See Section 13.1.1 for additional details.

¹⁷ This criterion was revised with global Protocol Amendment 5. See Section 13.1 for details.

¹⁸ Prior to global Protocol Amendment 5, luminal stenosis or occlusion was $\geq 50\%$. See Section 13.1 for details.

5. Patient has or is intended to receive an implantable ECG loop recorder
6. Indication for chronic anticoagulation based on guideline recommendations or investigator's judgment; e.g., patient with prosthetic mechanical valve, venous thromboembolism, hypercoagulable state
7. Indication for chronic antiplatelet therapy based on investigator's judgment, in which anticoagulation is not a reasonable substitute, or chronic therapy with a conventional non-steroid anti-inflammatory drug (NSAID) for a non-stroke indication
8. Hypersensitivity or any other contraindication listed in the local labeling for ASA or rivaroxaban
9. Active bleeding, major bleeding within last 6 months, high risk for serious bleeding contraindicating anticoagulant or antiplatelet therapy or history of primary intracranial hemorrhage¹⁹
10. Hepatic disease associated with coagulopathy (prothrombin time prolonged beyond the normal range) and clinically relevant bleeding risk including cirrhotic patients with Child Pugh B and C
11. Estimated glomerular filtration rate (eGFR) < 30 mL/min/1.73 m² as assessed at local laboratory within 1 month of screening
12. Life expectancy less than 6 months
13. Concomitant use of strong inhibitors of both cytochrome P450 isoenzyme 3A4 (CYP3A4) and P-glycoprotein (P-gp), i.e., human immunodeficiency virus protease inhibitors and the following azole-antimycotics agents: ketoconazole, itraconazole, voriconazole, or posaconazole, if used systemically

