7.1.2 Timing of assessments

7.1.2.1 Visit 1 (screening) - amended

Visit 1 will be used to assess the eligibility of the patient. After obtaining signed informed consent, the investigator will review the diagnostic tests required to diagnose ESUS. All diagnostic assessments for ESUS should be completed before the screening visit. If prolonged cardiac rhythm monitoring and/or echocardiography are not performed at time of screening, this can be done during the screening period. All acute therapies for stroke (e.g., thrombolysis) and diagnostic tests performed to diagnose acute stroke and ESUS will be recorded in the eCRF.²⁸

Demographic data (age, gender, race/ethnicity), weight (kg), height (cm), and medical history including reporting of stroke risk factors will be recorded at this visit. Laboratory assessments will include creatinine and eGFR (if not conducted at local laboratory within 1 month before screening, use value for eGFR as reported on laboratory report, otherwise calculate eGFR using MDRD formula, for which a calculator can be found for example on the internet www.mdrd.com) and pregnancy testing (only in women of childbearing potential). The modified Rankin score will be assessed as part of the exclusion criteria and NIHSS as part of the inclusion criteria.

The screening period will be 6 weeks maximum.²⁹

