7.6.1.4 Modified Rankin Score - amended

In addition to the regular assessments at screening, 1 year, and EOT, the Modified Rankin Score will be assessed by the investigator at 7 days or at discharge, if this occurs before 7 days, and again at 3-6 months⁴¹ after a recurrent stroke. The scale spans 0-6, perfect health without symptoms to death.

- 0 - No symptoms.
- 1 - No significant disability. Able to carry out all usual activities, despite some symptoms.
- 2 - Slight disability. Able to look after own affairs without assistance, but unable to carry out all previous activities.
- 3 - Moderate disability. Requires some help, but able to walk unassisted.
- 4 - Moderately severe disability. Unable to attend to own bodily needs without assistance, and unable to walk unassisted.
- 5 - Severe disability. Requires constant nursing care and attention, bedridden, incontinent.
- 6 - Dead.

8. Statistical methods and determination of sample size

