#### **4.5.4 Determination of baseline values**

Baseline is defined as the last non missing value until and including the day of randomization visit.

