#### **4.6 Determination of sample size**

The study is event-driven and it is estimated that 7000 patients (3500 per treatment group) need to be randomized in order to have approximately 450 patients experiencing a confirmed primary efficacy outcome event using the ITT data scope. This number of events will allow the demonstration of superiority of rivaroxaban compared to ASA with regard to the primary outcome with a power of 90% and a one-sided level of significance  $\alpha=0.025$  under the following assumptions:

- An average yearly event rate of the composite primary efficacy outcome of 3.8% in the ASA group (4.0% for patients with age  $\geq 60$  years, 2.0% for 10% of patients with age  $< 60$  years)
- Effect size: A 30% RRR for stroke and systemic embolism in the rivaroxaban group compared to ASA
- Length of the recruitment period is 2 years and the total study duration is 3 years

- Approximately 10% of patients will permanently discontinue study medication in the first year and 7% in following years
- Approximately 5% of patients with a diagnosis of AF will switch to standard treatment during study conduct
- Approximately 3% patient deaths per year and 1% of patients lost to follow-up per year

Under these assumptions the expected RRR to be observed in this study would be 26% for the primary efficacy outcome.

The number of patients enrolled may be adjusted and the study duration may be adapted based on a blinded review of the observed overall event rate of confirmed primary efficacy outcomes during the study.

Sample size estimation was based on a Statistical Analysis Software (SAS) macro provided by [Shih](#).

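### The exploratory Rankin test leaves the scheduled baseline score unused and does not say whether the end-of-treatment score or the change is ranked

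*SAP*

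**What the plan says.** SAP 6.5 (Other procedures and variables) gives the Rankin analysis in two sentences. The first is descriptive: "The score will be analyzed by frequency tables and bar charts comparing baseline to EOT". The second is the comparison of arms: "Wilcoxon rank-sum test will be used to give exploratory p-values comparing treatment groups". The population is set at the head of the section: "The analysis of other variables will be by treatment group and overall and based on ITT". No stratum, covariate, model or effect estimate is named. The age-group stratum used in the primary log-rank test and Cox model (SAP 6.2.4) is not carried over.

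The protocol collects a baseline value. Protocol 7.6.1.4 states: "In addition to the regular assessments at screening, 1 year, and EOT, the Modified Rankin Score will be assessed by the investigator". Protocol 7.1.2.1 ties the screening score to eligibility: "The modified Rankin score will be assessed as part of the exclusion criteria and NIHSS as part of the inclusion criteria". Exclusion criterion 1 in Protocol 5.1.2, "Severely disabling stroke (modified Rankin score" of 4 or more at screening), leaves 0 to 3 for eligible patients. SAP 4.5.4 makes that screening score the baseline: "Baseline is defined as the last non missing value until and including the day of randomization visit".

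**The concern.** A patient's Rankin score at EOT reflects both the disability left by the index stroke and whatever happened during follow-up. The first part is fixed before randomization and carries no information about treatment. A two-sample rank test on EOT scores counts it as noise, although a measure of it is already on file.

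The sentence also leaves the analysis open. It follows directly on a description of baseline against EOT, so a programmer could rank either the EOT score or the change. The two can give different p-values, and ranking the change treats a step from 0 to 1 like a step from 3 to 4.

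At stake is the precision of one exploratory comparison, and a line of the plan that two analysts could carry out differently. Bias and type I error are not in question.

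**Working it through.** **No plan figure to reproduce.** SAP 4.6 powers only the primary outcome. The documents give no effect size, power, baseline distribution or baseline-to-EOT correlation for Rankin. Everything below depends on an assumed correlation ρ.

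**Step 1: is the baseline likely to be prognostic?** SAP 4.6 assumes 3.8% primary events per year on aspirin and 3% deaths per year. The protocol synopsis plans a mean treatment duration of about 2 years.

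- Primary events: 3.8% × 2 = 7.6%.
- Deaths: 3% × 2 = 6%.
- Neither: at least 100 − 7.6 − 6 = 86.4%.

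For most patients, then, no recurrent stroke or death separates the two scores. This supports a positive ρ but does not give its size.

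**Step 2: variance under three analyses, relative to the EOT score.** Adjusting for baseline leaves 1 − ρ². The change score, with equal spread at both times, has 2(1 − ρ). Relative efficiency of adjustment against the raw EOT score is 1/(1 − ρ²).

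| Assumed ρ | Variance removed by adjustment | Left after adjustment | Change score | Relative efficiency |
|---|---|---|---|---|
| 0.2 | 4% | 0.96 | 1.6 | 1.04 |
| 0.3 | 9% | 0.91 | 1.4 | 1.10 |
| 0.4 | 16% | 0.84 | 1.2 | 1.19 |
| 0.5 | 25% | 0.75 | 1.0 | 1.33 |
| 0.6 | 36% | 0.64 | 0.8 | 1.56 |
| 0.7 | 49% | 0.51 | 0.6 | 1.96 |
| 0.8 | 64% | 0.36 | 0.4 | 2.78 |

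**Step 3: does ranking the change already do the job?** Let k be the ratio of baseline to EOT standard deviation. The change score then has relative variance 1 + k² − 2ρk, and

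(1 + k² − 2ρk) − (1 − ρ²) = (k − ρ)² ≥ 0.

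On this linear-score approximation the change is never more precise than adjustment. It is equal only when k = ρ.

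**Step 4: ordinal check.** Scores were simulated from correlated normal variables cut into categories, with 400,000 draws per scenario. Assumed inputs:

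- baseline 0–3 in shares 30/35/22/13% or 40/40/15/5%;
- EOT 0–5 in shares 32/33/18/10/5/2%;
- either no deaths, or 6% of patients (the figure from step 1) moved to score 6 independently of baseline.

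R² is the share of EOT rank variance explained by baseline category, which approximates what stratifying on baseline removes. Ranges span the two baseline distributions.

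| Latent correlation | R², no deaths | R², 6% scored 6 |
|---|---|---|
| 0.3 | 6.5–6.8% | 4.9–5.4% |
| 0.5 | 18.8–19.6% | 14.4–14.9% |
| 0.7 | 37.9–39.3% | 29.0–30.3% |
| 0.8 | 50.1–52.6% | 38.8–40.3% |

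Overall the range is about 5% to 53%. Cutting the scores into categories, limiting baseline to 0–3 and scoring deaths as 6 make the gain smaller than the simple formula suggests.

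**The case against.** **It is only an exploratory p-value.** The SAP says so, and the variable lies outside the primary and secondary efficacy outcomes and the sequential testing of SAP 6.2.5. Nothing is powered on it, and the plain test is valid under randomization. All of this stands, and it sets the priority.

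**Change may be what is ranked, in which case baseline is used.** The text allows that reading. Step 3 shows that it is no better than adjustment, and the fact that both readings are open is a reason to fix the sentence.

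**The correlation could be low.** Baseline is confined to four values. Under the planned timelines EOT falls roughly one to three years after randomization, and it takes in new strokes and possibly deaths. This stands, so the range above starts at ρ = 0.2.

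**The remedy has its own assumptions.** A proportional-odds model assumes a common odds ratio across cut-points and gives a conditional estimate. That is fair, and it is why the model is optional below. The van Elteren test does not need that assumption.

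**Deaths and missing EOT scores matter more.** SAP 6.5 describes a scale that runs to 6 for death, but gives no rule for patients who die without an EOT visit or lack an EOT score for other reasons. This is a separate gap in the same lines. Neither test resolves it, and it could change the result itself as well as its precision.

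**Conclusion.** The point holds as a free improvement of low severity. The Rankin comparison is unadjusted, the ranked quantity is not stated, and a baseline score of 0–3 is scheduled for every eligible patient. The direction of the gain is secure for any positive correlation. Its size is not known: about 4% to 64% of the variance for an assumed ρ of 0.2 to 0.8, or about 5% to 53% in the ordinal simulation under its assumed score distributions.

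Three stronger readings are tempting, and the documents support none of them.

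- A reader might infer that much of the variance is being left in. That requires a correlation of roughly 0.5 or more, and the documents give none.
- A reader might infer a definite gain in power. With no Rankin effect size in the plan, no power figure can be given for either test.
- A reader might infer that the trial's evidence on function rests on this test. Disabling stroke (Rankin 4 and 5) is a separate secondary efficacy variable, analysed as time to event (SAP 6.2.2 and 6.2.5), and is not affected. Nor is the primary result.

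**What to change.** Reword the Rankin line in SAP 6.5 to say that the EOT score is what is compared, and that the arms are compared with a van Elteren test stratified by baseline Rankin (0, 1, 2, 3). Any ineligible higher baseline score should be pooled into the top stratum, since SAP 6.1.4 foresees patients randomized despite meeting an exclusion criterion. The same sentence should say where a patient with no baseline score goes, so that the ITT basis is kept.

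Optionally, add a proportional-odds model with baseline Rankin and age group as covariates, reporting the common odds ratio with its 95% CI. Readers would then have an effect estimate beside the p-value. The p-values remain exploratory.

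The cost is about a line of SAP text and a small change to the code, made before treatment codes are opened. It needs no new data or visits and does not affect validity.
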